10.0 Local Number of Participants

10.1 Local Number of Participants to be Consented: We plan to analyze data from at least 150 target participants. Of these, 50 will bring friends as social buffers. Thus, we plan to enroll at least 200 children. To account for attrition between sessions/replacement for incomplete data, up to 300 children may be consented/enrolled.

11.0 Local Recruitment Methods

11.1 Recruitment Process: Families will be initially contacted by phone, email, or paper mail to invite them to participate. Paper mail will include the IRB-approved recruitment flyer. Interested families will be provided a more detailed overview of the study procedures in a telephone call. If the family is interested in participating, the parent will verbally complete a screening interview to assess inclusion and exclusion criteria, and for those who are eligible, the first visit will be scheduled. Copies of the consent and assent forms will be sent to families prior to the visit, along with directions to the University, and a reminder call will be a chance for families to confirm their interest in participation after having seen the consent forms. Souvenir brain images may be shared with families to increase interest. These images will only show a single cross-section of the brain.

Regarding recruitment of a friend: The family of the participant will contact the family of the friend make sure that they have permission to give us their contact information. Parents of the friend will then be contacted by telephone and/or email to provide an overview of the study and the role of the friend. The friend's parent will then be emailed a link to a consent & assent forms and MRI Safety Screening form (University of Minnesota REDcap) that they can complete and sign online before the session. If they do not respond to email in ~3 days, our recruiter will call them for a reminder. There will be phone and email contact information so that parents can ask any questions they have before their child comes to the lab. The assent form provided to the friend at the time of the study visit will also have a line that the parent of the main child participant can sign as a witness to the consent process. We are currently using this process successfully in STUDY00006288.

11.2 Identification of Potential Participants: Potential participants will be identified using the ICD registries of families interested in being contacted about research. These families have agreed to be contacted, and once ICD Registry procedures have been followed, including proof of IRB approval, an encrypted list is provided to study staff. Paper and electronic flyers will be posted to supplement the list, and these materials may be physically posted as flyers, or electronically distributed via social media or list-servs such as CEHD. The Community Engagement and Education (CEED) hub at the Masonic Institute for the Developing Brain (MIDB) will be used for consultation services to improve community engagement and recruitment

efforts. No protected records are involved. Study staff will make initial contact.

The Institute of Child Development Participant Pool or IPP does not contain data that generates new knowledge. Indeed, maintaining the contact information of parents who have voluntarily expressed interest in child development research has been classified by the IRB as “Not Human Research” as defined by DHHS and FDA regulations and informed by HRP-310.

11.3 Recruitment Materials: We will recruit via telephone, email, and paper mail (as parents have given us these three means of contacting them). We will also post flyers and put the flyer information on our website, other social media outlets, local organizations’ newsletters, and share via listserv so that families can contact us. Materials are uploaded in ETHOS.

11.4 Payment:

- Child Participant: \$40 debit or gift card for Visit 1; \$60 in debit or gift card for Visit 2; \$30 for optional actigraphy device
- Parent of Child Participant: \$25 in debit or gift card for Visit 1; \$25 in debit or gift card for Visit 2
- Friend of Child Participant: \$40 in debit or gift card for Visit 2

Cards will be given at the session to parent & child as specified. Where appropriate, due to remote buffering for example, we will mail cards. We intend to use Greenphire ClinCard prepaid debit cards for compensation and have included appropriate language in the consent document. We will provide a Target gift card instead of the ClinCard if parents object to the terms and conditions of the ClinCard.

12.0 Withdrawal of Participants

12.1 Withdrawal Circumstances: If participants are enrolled (consent signed) and subsequently determined to meet exclusion criteria, their data will be excluded from analyses. Children may be withdrawn from the study without their consent if we discover a safety concern for MRI scanning after consent/assent. Children may also be withdrawn if the experimenter believes that the child is excessively distressed by the affect paradigm or general MRI scanning procedures. Participants will receive full compensation for the session at which they are withdrawn.

12.2 Withdrawal Procedures: If participants voluntarily withdraw, we will verify permission to retain and use any data collected to that point. If participants wish to withdraw all permission, we will destroy any data collected from the participant but will keep their name in our study records

with a note that they withdrew. This procedure prevents us from inadvertently enrolling participants more than once. If the participant is withdrawn by the researcher, we will retain and use any data collected from the participant.

12.3 Termination Procedures: Data will not be used after termination.

13.0 Risks to Participants

Foreseeable Risks:

Questionnaires: Youth or parents may experience concerns when completing questionnaires dealing with symptoms of behavior problems. Any time one works with youth there is the possibility that they will reveal information about abuse and/or indicate that they are thinking of hurting themselves or others. We are mandated reporters, a fact that is revealed in both consent and assent forms. However, in over a decade of working with children and youth drawn from our participant files, we have never encountered a reportable incident, so we consider this risk to be very low.

Amygdala-activating Tasks. The tasks are designed to be uncomfortable, but not painful or distressing. Children encounter many types of affective stimuli in their everyday lives. Thus, we do not consider these stimuli to be out of the ordinary. To reduce risk, youth are told that they can always stop without prejudice if they choose. In addition, we carefully expose youth and their parents to example stimuli to ensure that all are comfortable with continuing.

MRI Scanning: The primary risks associated with magnetic resonance scanning involve risk of injury or burn in the event that unsafe metallic objects are introduced into the scanner environment. Loose items have the potential to become projectiles while stationary metallic surfaces could build heat over time and cause a burn. In addition, implanted medical devices could become non-functional or experience torque that could move metal implants through body tissue. All participants are screened multiple times for the presence of metal in or on the body. Final screening occurs immediately prior to MRI scanning.

There is no evidence for any long-term negative effect of MRI procedures on the body. The guidelines from the Bureau of Radiological Health (Food and Drug Administration) will be followed with regard to specific absorption rate (SAR) of energy (rf) and time-variant magnetic fields (dB/dt). All safety features of the clinically approved Siemens 3T scanner will be used to ensure that levels are well below the peripheral nerve stimulation threshold for both children and adults.

The MRI procedure involves exposure to a high level of noise while in the scanner environment. Participants are required to wear sound attenuating

PROTOCOL TITLE: An MRI Study of Learning and Social Support

VERSION DATE: v.10 2024.12.18

earplugs to protect their hearing. Beyond the risk to hearing, many participants find the scanner sounds annoying and monotonous. We provide additional headphones and/or foam padding over the top of the earplugs to further attenuate the background noise. This additional padding can become uncomfortable after long periods of time.

To reduce anticipatory stress for the scanner experience and to ensure that children feel comfortable with all MRI procedures, youth will complete a mock MRI scan in an MRI simulator. This pretend scanner has all of the primary features of the actual scanner, including an identically sized tunnel, the peripheral recording equipment, earplugs, headphones, video screen, audio system, button response box, and a speaker to play the scanner sounds around the tunnel, as if we were scanning, but with no magnetic field and no images produced.

Saliva Sampling. The saliva is collected on an absorbent swab. Any time anything is put in the mouth there is the risk of choking. This is a greater concern when participants are lying supine in the MRI environment.

However, we deliberately use long sponge rolls that hang out of the mouth during saliva collection. The child is instructed to hold on to the end sticking out of the mouth while chewing on the other end until it is soggy. The age of participants, 10-15 years, also reduces the risk of choking as these youth are better able to follow experimenter instructions and to realize when they are placing the sponge too far into their mouths to be comfortable.

13.1 Reproduction Risks:

The risks of strong magnetic fields for the developing human fetus are unknown. To protect against these unknown but potential risks, we will screen all female youth (including youth serving as the friend social buffer) who have started menstruating for possible pregnancy. In addition, if buffers are in-person, they will be screened for possible pregnancy and exclude women who think they could be pregnant from serving as the social buffer (i.e., sitting in the MRI scanner room with the child).

13.2 Risks to Others: N/A

14.0 Potential Benefits to Participants

14.1 Potential Benefits: This study confers no direct benefits to participants.

15.0 Statistical Considerations

15.1 Data Analysis Plan:

Preliminary Analyses to Determine Covariates Needed for Primary Analyses.

The purpose of collecting data on potential covariates is to identify variables

that are correlated with both the independent variable (social buffering condition, sex, pubertal stage) and the primary outcome measures. Those covariates that are associated with the independent and outcome variables will be controlled for in the primary analyses. Those that are not will be used to describe the sample, but will not need to be included in the analyses to obtain unbiased estimates. For each potential covariate, we will conduct correlations or t-tests with pubertal stage, and t-tests, ANOVAs, or chi-square tests (as appropriate) with sex and condition. If data do not confirm to modeling assumptions, we will use nonparametric analogs instead.

Preliminary Analyses of Imaging Data to Yield Primary Outcome Measures: fMRI data will be analyzed in FSL software (version 6.0.1) to generate voxel-wise contrast maps. Mean signal values will be extracted from these maps in a priori regions of interest for every participant using the methods described below. These preliminary analyses are used to generate the fMRI outcome variables of interest. The values of these outcome variables for each participant will be used in the general statistical analyses described in the next section. In total, these preliminary analyses will yield 6 primary task-related outcome variables, and 6 primary connectivity-related outcome variables.

Task-based analysis: In first level analyses (single subject), brain activity will be modeled for each participant using a voxel-wise multiple regression analysis with a task predictor (aversive image vs. safe image), 24 regressors for head motion (Satterthwaite et al., 2013) and additional regressors to model censored data points (motion spikes). In subsequent analyses, we will explore the utility of including other time varying individual differences variables (e.g., heart rate, respiration) that are known to contribute to the BOLD signal. However, since these measures are expected to vary by stress condition, removing the effects of these physiological variables may unintentionally remove effects of interest. Particular care will be taken to reduce the confound of head motion by censoring (identifying as artifact) any data point with absolute motion greater than 2 mm (1 voxel) or a framewise displacement greater than 1 mm (1/2 voxel), as well as the immediately preceding and following data points. Data points with DVARS values exceeding the individual's 75th percentile plus two times the interquartile range will also be censored. Participants with more than 25% of data points censored for artifact will be excluded from further analyses. This analysis will be used to identify brain regions differentially activated by aversive learning. Based on prior literature, we will examine activation in 5 a priori regions of interest, including "pain-related" brain regions (dorsal anterior cingulate [dACC], left and right anterior insula) and "safety-related" or regulatory brain regions (ventromedial prefrontal cortex [vmPFC], and left and right dorsolateral prefrontal cortex [dlPFC]). For each subject, the

mean percent change in MR signal (averaged across voxels) between aversive face/shape and the safe face/shape will be extracted from each of these 6 regions. This analysis will generate the 6 task-related brain activation outcome variables (listed in section 4.3) for each participant.

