
Pubertal Development: We will create a summary pubertal development index from parent & child report. A planned nurse exam was dropped due

to COVID and funding considerations. Parents & youth will complete the Morris and Udry (1980) pubertal development questionnaire, which allows placement in Tanner stages for hair, testicles, and breast development.

Questionnaires.

Demographic Questionnaire: Parents will complete information on pre-tax family income, education level of parent(s), composition of the household, and medications that the child regularly takes.

Daily Diary: The parent and the youth both will report the following for the child that day: the time of wake up, medication usage, illness/fever, physical activity, and caffeine consumption.

Relationship Quality: Youth and their friend (when assigned to friend buffer condition) will complete the Network of Relationships Inventory (NRI, Furman & Buhrmester, 2009) for parents and their close friend. This questionnaire is based on an integration of attachment and Sullivanian theory and assesses three systems that are expected to be key in close relationships: attachment, caregiving and affiliation. The scales are: companionship, seek safe haven, seek secure base, provide safe haven, provide secure base, conflict, antagonism and criticism. We will also include the full set of scales from the NRI,: Each scale consists of 3 items scored on a 5-point Likert scale. Psychometric qualities are high. Condition differences in quality of relationships will be examined and included as covariates if groups differ significantly. Otherwise, in follow-up analyses we will examine whether social buffering effects are stronger in relationships the child views as more supportive.

MacArthur Health and Behavior Questionnaire (HBQ) for 9-18 Year-Olds (Parent and Child, 2.1): This questionnaire was developed by Marilyn Essex based on the original HBQ for 4-8 year olds. We have used it many times. The scales we proposed to use here have high reliabilities (Cronbach alpha's > .8). We will use the peer scales (acceptance/rejection, bullied, relational victimization, asocial, behavioral inhibition) and broad-band symptoms scales (Internalizing, Externalizing). These measures will be examined for balance across groups and if differences by condition, pubertal stage, or sex are found, will be entered as covariates.

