State-Trait Anxiety Index: A brief scale to assess current and general anxiety, which might be an important covariate.

Self-Report of Stress: As a manipulation check, participants will rate their arousal and emotional state at various points during Visit 2.

Morris and Udry Pubertal Development Questionnaire: The parent and youth will both report on hair, testes, and breast development.

Responses to Stress Questionnaire: Includes a checklist of stressors and how often they have occurred recently, then asks how respondents coped with each stressor listed and what coping methods were used more often.

Child Life Events Inventory: Parent reports on past significant events in the child's life that may have caused trauma, stress, or other relevant outcomes.

Sleep Diary: Child reports on daily sleep habits over several days including timing of falling asleep and waking, perceived sleep quality, and sleep disruptions. This sleep diary would be completed once a day for up to 14 days.

Perceived Stress Scale: Child reports on perceptions of life stress over the past month.

Child Life Challenges: Parent reports on their child's global lifetime adversity exposure.

Child Life Challenges: Child reports on their global lifetime adversity exposure.

Physiological Measures.

Stress Hormones: We will assay saliva samples for stress sensitive hormones: cortisol and alpha-amylase. Saliva will be collected using SalivaBio Oral Swabs (SOS) or passive drool and stored frozen at -20°C until shipped for assay. Medications will be recorded from parent report and classes of drug codes will be used to group meds by presumed mechanisms of action and will be entered as covariates (Granger et al., 2009). Systemic glucocorticoid medications are an exclusion criterion. For each analyte, we will calculate area under the curve from intercept (AUCi) to provide a single measure for the main analysis.

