Hair Hormones: Hair will be assayed for a full panel of stress, puberty, and sleep hormones. Hair cortisol provides a measure of the stress sensitive hormone cortisol indexed over approximately 3 months. We will take the ~ 3 cm of hair next to the scalp on the posterior vertex. Based on an average hair growth rate of 1 cm/month, this represents hair grown over the 3-month period prior to sampling. Wash and steroid extraction procedures will be conducted in [name]'s ISO lab, following their published protocol (Stalder & [name], 2012, study II) with 7.5 mg of hair used for analysis. Participants will also complete a questionnaire about hair products and treatment that can be included as covariates. We anticipate that we will not be able to collect hair cortisol for some participants whose hair is too short or who refuse this sampling. In previous work, we have

had missing samples for ~ 10% of participants. We will deal with this using multiple imputation by chained equations (MICE) to impute missing data.

Physiological Recording: Participants will wear a combination of standard Siemens physiological recording equipment for the MRI environment (respiration belt, pulse oximeter, EKG leads). In addition, they will wear BioPac MRI-safe skin conductance electrodes. Samples will be collected throughout the entire MRI scan. Response measures will be computed by regressing aversive learning condition values on comparison values during the resting state scan and saving the residual as the response measure. If the parent and child opt-in, the child will wear an actigraphy device for several days. The actigraphy device uses accelerometers and gyroscopes to measure body movement. After completion of actigraphy data collection, the parent will return the device back to the researchers.

All questionnaires and surveys are included in the ETHOS portal. Contact information and child age will be obtained from an existing registry of families who have expressed interest in child development research (specifically, parent name(s), address, phone number, email address, child name, child sex, and child birthdate). All other data will be acquired directly from the participants, and information obtained from the participant registry will be verified verbally with the parent. Birthdate will be collected from parent at the session so that a precise age of child can be obtained.

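### The covariate screening rule usually drops variables that predict the outcome but are unrelated to condition, sex and puberty, which forgoes precision; a short fixed list would recover it

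*Combined protocol and SAP*

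**What the plan says.** Section 15.1 makes entry depend on association with an independent variable (condition, sex or pubertal stage) and with the outcome: "Those covariates that are associated with the independent and outcome variables will be controlled for in the primary analyses". For the remainder it says: "Those that are not will be used to describe the sample, but will not need to be included in the analyses to obtain unbiased estimates". The screening tests it lists are against the predictors, beginning "For each potential covariate, we will conduct correlations or t-tests with pubertal stage" and going on to sex and condition. It names no test against the outcome and no threshold.

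Section 5.2 words entry differently for particular instruments:
- HBQ scales: "if differences by condition, pubertal stage, or sex are found, will be entered as covariates".
- Relationship quality: "Condition differences in quality of relationships will be examined and included as covariates if groups differ significantly".
- Medication classes, for the hormone outcomes, are "used to group meds by presumed mechanisms of action and will be entered as covariates", with no test at all.

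Section 15.2 allows for 12 covariates and treats them only as a cost: fewer covariates are said to give a smaller detectable effect. Sex and pubertal stage are terms of the primary models in their own right (Section 15.3).

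**The concern.** The rule is built to remove confounding. For sex and pubertal stage, which are not randomised, that is a proper aim. For condition it is not the relevant question. A variable fixed before allocation is known can differ between conditions only by chance, and a significance test finds only that chance difference. In a linear model a covariate sharpens the condition contrast because it predicts the outcome, whether or not it is balanced. The reason given, that such variables "will not need to be included in the analyses to obtain unbiased estimates", is true for the condition effect but says nothing about its standard error.

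Two things are at stake. The first is power that already-collected data could supply. The second is a primary model that is not fixed in advance: one leg of the rule is association with the outcome, so the covariate set can differ between outcomes, and Sections 5.2 and 15.1 could lead two analysts to different models.

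**Working it through.** **Inputs.** From the documents: at least 150 analysed, of whom 50 bring friends (Section 10.1); three conditions; 12 covariates, α = .05 and power .80 (Section 15.2). Assumed: 50 per arm, p < .05 for each screening test, and a range of R² for the covariates.

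**1. The plan's own figure.** Solve the noncentral F for f², with λ = f²(u + v + 1). With u = 3 and v = N − 4 this gives 0.0556 at N = 200 and 0.0699 at N = 160, which round to the stated 0.056 and 0.070. With three conditions and all 12 covariates (u = 2, v = N − 24) it gives 0.0548 and 0.0709, within about 2% of the stated values.

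**2. How often the rule keeps a useful covariate.** If the covariate is unrelated to all three predictors, the chance of passing at least one predictor test is 1 − 0.95³ = 14.3%. It must then also test as associated with the outcome. In simulations with 12 candidates, of which three are prognostic, a prognostic covariate was kept about 6–14% of the time.

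**3. What adjustment is worth.** The SE of a condition contrast is multiplied by √(1 − R²). For a two-group comparison at 50 per arm, without multiplicity adjustment:

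| R² | SE factor | Detectable difference (SD) | Power at 0.5 SD |
|---|---|---|---|
| 0 | 1.000 | 0.560 | 70.5% |
| .10 | 0.949 | 0.532 | 75.0% |
| .20 | 0.894 | 0.501 | 79.8% |
| .30 | 0.837 | 0.469 | 84.8% |

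**4. What the rule loses.** Simulated power of the omnibus condition test at n = 150, with a 0.5 SD effect in one arm and covariates independent of the predictors:

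| Setting | R² | Plan's rule | Fixed adjustment |
|---|---|---|---|
| One covariate | .10 | 72.2% | 76.2% |
| One covariate | .25 | 73.7% | 85.3% |
| Three prognostic of 12 | .12 | 73% | 77% |
| Three prognostic of 12 | .27 | 74% | 85% |

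A separate run of the three-of-12 setting gave losses of about 3, 4 and 8 points at R² = .06, .12 and .27 for the condition test. For the three-way interaction, which Section 15.3 tests first, they were about 0, 4 and 8 points.

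**5. When covariates correlate with puberty.** With assumed correlations of .2–.3, the rule kept them 33–96% of the time and the loss fell to about 0–4 points. At r = .3 and R² = .27, power was 86% under both the rule and the fixed model.

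**6. Type I error under the rule.** It was 5.1%, 4.8% and 3.4% at R² = .10, .25 and .50 (one covariate).

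**7. Cost in degrees of freedom.** The three-condition, three-way model has 12 parameters, so v = 150 − 12 = 138 without covariates, 135 with three and 126 with twelve. With u = 2 the detectable f² is 0.0698, 0.0714 and 0.0765. Break-even R² is 1 − 0.0698/0.0714 = 2.2% for three covariates and 1 − 0.0698/0.0765 = 8.8% for twelve.

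**The case against.** The strongest reply is that much of the adjustment is already in the plan. Sex and pubertal stage are model terms, and medication classes enter the hormone models untested. Physiological responses are formed by "regressing aversive learning condition values on comparison values during the resting state scan and saving the residual as the response measure", and cortisol and alpha-amylase are summarised as an area measured from the starting level. Screening against sex and puberty also serves confounding control, which matters because the hypotheses concern waning with puberty. All of this stands and limits the loss.

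The size is also open to challenge. The low retention follows from assuming independence from all three predictors; age, trait anxiety or internalizing scores may well correlate with puberty or sex. The threshold is assumed: at p < .20, independent covariates are kept 43–49% of the time. The comparator contains the right three variables, which nobody knows in advance. Fixing all 12 candidates gave 71% against 72% for the rule at R² = .06, 76% against 75% at .12, and 83% against 73% at .27. So there is no real gain at R² of .12 or below. This too stands, and it argues for a short list.

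The Section 5.2 wording could be read as the balance step of the Section 15.1 rule, described instrument by instrument. That is possible, but the text says that HBQ and relationship-quality scales enter on a difference alone, so it needs aligning.

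A reader might infer that the rule biases the condition effect or produces false positives. The documents do not support that: condition is randomised, and simulated type I error was at or below about 5%. Nor do they support the inference that every prognostic baseline variable is discarded, given the exceptions above.

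**Conclusion.** The concern holds as a loss of precision and an incompletely fixed primary model; validity is not at issue. The loss falls on covariates that predict the outcome and are unrelated to condition, sex and puberty. At n = 150 and p < .05, against a well-chosen three-covariate model, it is about 3–4 power points at R² of .06–.12 and 8–11 at about .27 for the condition test. It is little or nothing when the covariates also track puberty. The documents give no R² for any outcome, so it would go too far to read the larger figures as the expected loss. The differing entry rules in Sections 5.2 and 15.1 need reconciling whatever the R².

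**What to change.** Replace the screening rule in Section 15.1 with one short fixed covariate list per outcome family, about 3–5 variables and not all 12. Set it before outcomes are examined by condition, and use it whatever associations are observed.

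- Choose variables already collected that are expected to predict the outcome and that allocation cannot affect. Examples are age, time since waking for cortisol, and trait anxiety or HBQ internalizing if completed before the family knows the allocation. That condition matters because one Visit 1 parent form already depends on the assigned condition (Section 5.1).
- Include any variable needed to control confounding of the puberty and sex effects. Sex and puberty themselves need no listing.
- Do not list first-sample cortisol unless it is taken before the allocation is known; saliva is collected at Visit 2.
- Align the HBQ, relationship-quality and medication statements in Section 5.2 with the list, and keep balance tests as description only.

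The cost is SAP wording and a few degrees of freedom. Three covariates raise the detectable f² from about 0.070 to 0.071 at n = 150, repaid once they explain about 2% of residual variance. This is a cheap improvement, though not an unconditional gain.
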